## 14.2 Reference Safety Information

The Reference Safety Information (RSI) is the identified section of the Investigator Brochure (IB) or Summary of Product Characteristics (SmPC) used for assessing the causality and expectedness of an adverse reaction.

The RSI in this trial is defined as:

- Section 4.8 of the trial-supplied SmPC for ibrutinib tablets
- Section 4.8 of the trial-supplied SmPC for ibrutinib capsules

The versions of the above SmPCs are to be used for the purposes of pharmacovigilance reporting (in the case of this trial, for determining causality of an event) will be supplied to sites by the CTRU i.e. it is not necessarily the most recent available version online.

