# 14 PHARMACOVIGILANCE PROCEDURES

## 14.1 General definitions

The standard definitions are derived from the document 2011/C 172/01 ‘Detailed guidance on the collection, verification and presentation of adverse event/reaction reports arising from clinical trials on medicinal products for human use (“CT-3”)’ (based on the Clinical Trials Directive 2001/20/EC) and from the CIOMS Working Group VII definitions.

Term	Definition
Adverse Event (AE)	
Any untoward medical occurrence in a patient or clinical trial subject administered a medicinal product and which does not necessarily have a causal relationship with this treatment.
 
An adverse event can therefore be any unfavourable and unintended sign (including an abnormal laboratory finding, for example), symptom or disease temporally associated with the use of a medicinal product, whether or not considered related to the medicinal product.

Adverse Event of Special Interest (AESI)	
An adverse event of special interest (serious or non-serious) is one of scientific and medical concern specific to ibrutinib, for which ongoing monitoring and rapid communication by the investigator to the sponsor could be appropriate. Such an adverse event might require further investigation in order to characterise and understand it. Depending on the nature of the adverse event, rapid communication by the trial sponsor to other parties (e.g. regulators) might also be warranted.

Adverse Reaction (AR)	
All untoward and unintended responses to an IMP related to any dose administered.
 
This definition covers also medication errors and uses outside what is foreseen in the protocol, including misuse and abuse of the product.
 
This definition implies a reasonable possibility of a causal relationship between the event and the IMP. This means there are facts (evidence) or arguments to suggest a causal relationship.

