#### **14.4.4 SAEs and SARs**

All SAEs must be recorded on the electronic Serious Adverse Event Report eCRF within 24 hours of the research staff becoming aware of the event, from registration until 30 days post the last dose of study drug.

All SARs occurring for the duration of the trial must be recorded on the electronic Serious Adverse Event Report eCRF within 24 hours of the research staff becoming aware of the event. SARs will be reported from the date of first study dose and for the duration of the trial.

Each SAE/SAR will be described by:

- symptoms / diagnosis
- case description
- duration (start and end dates; times, if applicable)
- seriousness criteria
- action taken in relation to IMPs
- outcome
- causality, in the opinion of the investigator\*

*\*Assessment of causality must be made by a clinician. If a clinician is unavailable, initial reports without causality assessment should be submitted to the CTRU without a clinician's assessment within 24 hours, but must be followed up by medical assessment as soon as possible thereafter.*

When determining the expectedness of an event, please refer to the Reference Safety Information (RSI) (see Section 14.2)

The CTRU will be responsible for determining expectedness for each event in line with the RSI.

Please ensure that each SAE/SAR event is reported separately and not combined on one SAE/SUSAR form.

Changes in SAE outcome, seriousness criteria, causality, or significant / medically relevant changes to the event (key data) should be reported within 24 hours of becoming aware. Other follow up information should be added to the SAE/SUSAR eCRF when the event has reached a final outcome.

Events will be followed up until the event has resolved or a final outcome has been reached. Investigators must report all SAEs to their host institution in line with their local arrangements.

Refer to the Pharmacovigilance SSOP for SAE and SAR reporting.

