#### **14.4.5 SUSARs**

All SARs assigned by the CTRU as being unexpected (in line with the RSI) will be classified as SUSARs and will be forwarded to the CI/TMG delegates for review and subject to expedited reporting to the relevant regulatory authority.

Following the assessment of unexpectedness, the CTRU will request the site research team complete any additional information on the electronic Serious Adverse Event Report eCRF within 24 hours. The CTRU will inform the relevant regulatory authority, the Research Ethics Committee (REC) and the Sponsor of SUSARs within the required expedited reporting timescales. SUSARs will be sent to relevant pharmaceutical companies at the same time as submission to the relevant regulatory authority. **SUSARs are reportable from the date of first study dose and for the duration of the trial.**

Changes in SUSAR outcome, seriousness criteria, causality, or significant / medically relevant changes to the event (key data) should be reported within 24 hours of becoming aware. Other follow up information should be added to the SAE/SUSAR eCRF when the event has reached a final outcome. Events will be followed up until the event has resolved or a final outcome has been reached. Investigators must report all SUSARs to their host institution in line with their local arrangements.

Refer to the Pharmacovigilance SSOP for SAE and SAR reporting.

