## **14.6 Pharmacovigilance responsibilities**

### **14.6.1 Local Principal Investigator**

- Checking for AEs/ARs, SAEs and AEoSI during treatment/follow up's;
- Ensuring that AEs and ARs are recorded and reported to the CTRU in line with the requirements of the protocol.
- Using medical judgement in assigning seriousness and causality to SAEs/SUSARs, using the RSI approved for the trial;
- To ensure that the trial team are using the correct version of the safety reference documents;
- To ensure all SAEs, SARs (including SUSARs) and AEoSIs are recorded and reported to the CTRU within 24 hours of becoming aware and to provide further key follow up information within 24 hours. To ensure that reported events are chased with the CTRU if a confirmation of receipt is not received within 2 days of reporting.
- To report SAEs to local committees in line with local arrangements.
- In the case of pregnancy, to ensure that treatment is stopped immediately (in female participants) and the pregnancy is reported to the CTRU within 24 hours of becoming aware.

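### Sections 14.2 and 14.6.1 tell sites to judge causality from the Reference Safety Information, against 14.1 and 14.4.4, so unlisted serious reactions may be under-classified and miss SUSAR status

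*Protocol*

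**What the plan says.** Protocol 14.2 describes the RSI in general as the document "used for assessing the causality and expectedness of an adverse reaction". It identifies it as "Section 4.8 of the trial-supplied SmPC for ibrutinib tablets", with the same section of the capsule SmPC alongside. It then says that the versions sent to sites are, "in the case of this trial, for determining causality of an event", and that they need not be the latest ones online.

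Protocol 14.6.1 gives the local Principal Investigator this duty: "Using medical judgement in assigning seriousness and causality to SAEs/SUSARs, using the RSI approved for the trial".

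Protocol 14.4.4 asks sites to report "causality, in the opinion of the investigator" and adds: "Assessment of causality must be made by a clinician". It refers to the RSI for expectedness and makes the CTRU responsible for that decision.

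Protocol 14.4.5 sets the route to expedited reporting: "All SARs assigned by the CTRU as being unexpected (in line with the RSI) will be classified as SUSARs".

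Protocol 14.1 explains what makes an event a reaction: "This definition implies a reasonable possibility of a causal relationship between the event and the IMP". The same entry asks for facts or arguments that suggest causation. It does not ask whether the event is already listed.

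**The concern.** Causality and expectedness are separate judgements. A SUSAR needs an event that is serious, suspected to be caused by the drug, and not consistent with the RSI. If absence from section 4.8 counts against relatedness, the feature that would make a reaction unexpected also makes it less likely to be called a reaction.

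SUSAR status leads to expedited reporting to the regulator and ethics committee (14.4.5) and to real-time DMEC review (Appendix 10). Unlisted late effects matter in this trial. Randomised participants enter after at least 36 months of ibrutinib, or after 6 years if they come from FLAIR (8.1). They may be on treatment for up to 9 more years (14.5), and section 6.3 itself notes that the approval trials had relatively short follow-up.

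**Working it through.** No figure in the plan bears on this point, so the check is a comparison of the sections.

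1. **Is the causality wording a single slip?** No. It appears in the general description of the RSI in 14.2, in the trial-specific remark in 14.2, and in the investigator's duty in 14.6.1.

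2. **Does it conflict with other sections?** Yes.

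| Question | 14.2 and 14.6.1 | 14.1 and 14.4.4 |
|---|---|---|
| What decides causality? | The RSI, with medical judgement in 14.6.1 | A clinician's opinion on a reasonable possibility, from facts or arguments |
| What is the RSI for? | Causality and expectedness; for the versions sent to sites, causality | Expectedness |
| Who applies the RSI? | The site | The CTRU |

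A fixed version that may not be current suits an expectedness check. For causality, it points sites to a possibly outdated list.

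3. **What follows for an unlisted serious event?** There are two paths.
   - The site calls it related. It is a SAR, the CTRU finds it unexpected, and it becomes a SUSAR under 14.4.5.
   - The site calls it not related because it is not listed. It remains an SAE. The CTRU may still mark it unexpected, since 14.6.2 covers all SAEs, but 14.4.5 is worded for SARs only.

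4. **Can the second path be corrected centrally?** Only in part. The Chief Investigator or delegate reviews all SAEs and SARs (14.6.3). The stated power to assign causality, however, applies where no local assessment could be obtained. No power to change a local 'not related' is stated.

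5. **Does central review see every such event?** No. Under 14.4.4, SAEs are recorded from registration to 30 days after the last dose, while SARs are recorded for the duration of the trial. After 30 days, the site's causality call decides whether the event is reported as serious at all. Adverse events of any cause are collected to 60 days (14.4.1), and deaths are always notified (13.12). A non-fatal, unlisted event called unrelated after day 60 therefore has no adverse-event reporting route.

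**The case against.** The strongest reply is that this is loose drafting with little effect. No section says that an unlisted event must be called unrelated, and looking up known reactions is a legitimate input to a causality judgement. Section 14.6.1 opens with medical judgement, and its RSI phrase also covers seriousness, which section 4.8 cannot decide. The reporting section, 14.4.4, has the rule right. Every SAE in the window is reported within 24 hours whatever its cause, the CTRU assesses the expectedness of all of them, the Chief Investigator reviews them, and the DMEC sees cumulative data by arm with individual listings (20.3). Major haemorrhage is reported within one working day with no causality test (14.4.2). The Pharmacovigilance SSOP, to which sites are sent, is not at hand and may already be correct.

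Most of this stands, and it rules out three stronger readings that a reader might infer:

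- **That an unlisted event can never reach SUSAR review.** The protocol contains no rule equating unlisted with unrelated, and a clinician who applies 14.1 or 14.4.4 would call a plausible unlisted reaction related.
- **That the expected number of SUSARs is zero.** The SUSAR definition in 14.1 also covers a listed reaction of inconsistent severity, and reports that add significant information on the specificity, occurrence or severity of a known serious reaction.
- **That a formal comparison between arms is distorted.** Section 19.4.2 summarises rates by arm without specifying a test, and SAE rates do not depend on causality.

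What the reply does not remove is the contradiction itself, or the gaps in central power over causality and in reporting after 30 days.

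**Conclusion.** The contradiction is established from the text: 14.2 and 14.6.1 assign the RSI a role in causality that 14.1 and 14.4.4 do not give it. The consequence is a risk that unlisted serious reactions are under-classified and miss SUSAR status. It is not a certainty.

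The size cannot be computed. It depends on how many investigators treat absence from section 4.8 as evidence against causation, and on how often unlisted reactions occur. The documents give neither. The exposure is greatest more than 30 days after the last dose, where central review of SAEs no longer acts as a backstop for events called unrelated.

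The conclusion assumes that the Pharmacovigilance SSOP does not already override the protocol wording. Since this is a stated safety rule and the remedy is short, it should be corrected.

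**What to change.** - **Section 14.2:** describe the RSI as the reference for expectedness only, and change the trial-specific remark so that the supplied versions are for determining expectedness, as assessed by the CTRU.
- **Section 14.6.1:** remove the closing reference to the RSI from the seriousness and causality duty. State that causality follows the reasonable-possibility test of 14.1 whether or not the event is listed.
- **Pharmacovigilance SSOP:** check that it says the same, and amend it if it does not.

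The cost is a wording change in two sections and possibly the SSOP. The downside is that a few more events may be classed as SARs or SUSARs and need expedited handling.

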## 14.3 Operational definition – Serious Adverse Events (SAEs)

### 14.3.1 Events not classed as SAEs

The following events will not be recorded as SAEs within this trial:

- Hospitalisation for:
  - *Routine treatment or monitoring of the studied indication not associated with any deterioration in condition*
  - *Treatment which was elective and pre-planned, for a pre-existing condition not associated with any deterioration in condition*
  - *Admission to hospital or other institution for general care, not associated with any deterioration in condition*
  - *Treatment on an emergency, out-patient basis for an event not fulfilling any of the definitions for serious as given above and not resulting in hospital admission*
  - *Active Disease (this should be reported on the Active Disease eCRF)*
- Deaths attributable to CLL beyond 60 days of the last administration of trial IMP. These should be reported on the Death eCRF.

## 14.4 Recording and reporting AEs, SAEs, and SUSARs

Due to the nature of CLL and its treatment, participants are likely to experience several adverse events throughout the course of the disease.

Events will be reported on the eCRF using Medical Dictionary for Regulatory Activities (MedDRA) term(s) where possible and graded according to the National Cancer Institute Common Terminology Criteria for Adverse Events 5.0 (NCI-CTCAE). A copy is provided in the Investigator Site File and may be obtained at:

[https://ctep.cancer.gov/protocoldevelopment/electronic\\_applications/docs/CTCAE\\_v5\\_Quick\\_Reference\\_5x7.pdf](https://ctep.cancer.gov/protocoldevelopment/electronic_applications/docs/CTCAE_v5_Quick_Reference_5x7.pdf)

MedDRA coding of events will be performed centrally at the CTRU.

Should an event fulfil any of the Serious Adverse Event criteria described in Section 14.1, a serious adverse event eCRF should also be completed.

### 14.4.1 AEs and ARs

AEs may be spontaneously reported by the participant and/or in response to an open question from study personnel or revealed by observation, physical examination, or other diagnostic procedures, and should be reviewed at each cycle of protocol treatment. Any clinically relevant deterioration in laboratory assessments or other clinical finding is considered an AE, whether or not it is considered related to the IMP, if it meets the criteria of an AE or causes a change in the action taken.

When possible, signs and symptoms indicating a common underlying pathology should be noted as one comprehensive event.

All adverse events, both related and unrelated to CLL treatment will be collected on the relevant eCRF from trial registration until 60 days after the last dose of protocol treatment.

### 14.4.2 AEs of Special Interest (AESIs)

Both SAEs and AE of Special Interest should be collected and reported to Janssen (via CTRU) within one working day. AESIs in this study are:

Major Hemorrhage  
defined as:

- Any treatment-emergent hemorrhagic AE of Grade 3 or higher.\*
- Any treatment-emergent SAE of bleeding of any grade.
- Any treatment-emergent CNS hemorrhage/hematoma of any grade.

\*All hemorrhagic AEs requiring a transfusion of red blood cells should be reported as a Grade 3 or higher AEs per NCI-CTCAE Version 4.03.

### 14.4.3 Special Situations

The following special situations should be collected and reported to Janssen (via the CTRU) within one working day, with or without an associated (SAE):

- exposure to ibrutinib during pregnancy (paternal, maternal)
- suspected transmission of any infectious agent via administration of ibrutinib
- Overdose of ibrutinib
- Exposure to ibrutinib whilst breastfeeding
- Suspected abuse/misuse of ibrutinib
- Inadvertent or accidental exposure to ibrutinib
- Any failure of expected pharmacological action (i.e., lack of effect) from ibrutinib
- Medication dispensing error (includes potential, intercepted or actual) involving ibrutinib (with or without patient exposure to the Janssen Product(s) e.g., name confusion)
- Unexpected therapeutic or clinical benefit from ibrutinib

#### **14.4.4 SAEs and SARs**

All SAEs must be recorded on the electronic Serious Adverse Event Report eCRF within 24 hours of the research staff becoming aware of the event, from registration until 30 days post the last dose of study drug.

All SARs occurring for the duration of the trial must be recorded on the electronic Serious Adverse Event Report eCRF within 24 hours of the research staff becoming aware of the event. SARs will be reported from the date of first study dose and for the duration of the trial.

Each SAE/SAR will be described by:

- symptoms / diagnosis
- case description
- duration (start and end dates; times, if applicable)
- seriousness criteria
- action taken in relation to IMPs
- outcome
- causality, in the opinion of the investigator\*

*\*Assessment of causality must be made by a clinician. If a clinician is unavailable, initial reports without causality assessment should be submitted to the CTRU without a clinician's assessment within 24 hours, but must be followed up by medical assessment as soon as possible thereafter.*

When determining the expectedness of an event, please refer to the Reference Safety Information (RSI) (see Section 14.2)

The CTRU will be responsible for determining expectedness for each event in line with the RSI.

Please ensure that each SAE/SAR event is reported separately and not combined on one SAE/SUSAR form.

Changes in SAE outcome, seriousness criteria, causality, or significant / medically relevant changes to the event (key data) should be reported within 24 hours of becoming aware. Other follow up information should be added to the SAE/SUSAR eCRF when the event has reached a final outcome.

Events will be followed up until the event has resolved or a final outcome has been reached. Investigators must report all SAEs to their host institution in line with their local arrangements.

Refer to the Pharmacovigilance SSOP for SAE and SAR reporting.

#### **14.4.5 SUSARs**

All SARs assigned by the CTRU as being unexpected (in line with the RSI) will be classified as SUSARs and will be forwarded to the CI/TMG delegates for review and subject to expedited reporting to the relevant regulatory authority.

Following the assessment of unexpectedness, the CTRU will request the site research team complete any additional information on the electronic Serious Adverse Event Report eCRF within 24 hours. The CTRU will inform the relevant regulatory authority, the Research Ethics Committee (REC) and the Sponsor of SUSARs within the required expedited reporting timescales. SUSARs will be sent to relevant pharmaceutical companies at the same time as submission to the relevant regulatory authority. **SUSARs are reportable from the date of first study dose and for the duration of the trial.**

Changes in SUSAR outcome, seriousness criteria, causality, or significant / medically relevant changes to the event (key data) should be reported within 24 hours of becoming aware. Other follow up information should be added to the SAE/SUSAR eCRF when the event has reached a final outcome. Events will be followed up until the event has resolved or a final outcome has been reached. Investigators must report all SUSARs to their host institution in line with their local arrangements.

Refer to the Pharmacovigilance SSOP for SAE and SAR reporting.

**Contact details for queries relating to SAEs / SUSARs**  
**Email: [ctru\\[contact]](mailto:[contact])**

#### **14.5 Pregnancies or suspected pregnancies**

Pregnancy in participants on trial treatment must be prevented as effectively as possible. As participants could be on treatment for up to 9 years, it is important to provide regular pregnancy counselling about highly effective contraceptive measures and document these discussions in the medical notes. All guidance regarding contraception, pregnancy and breast-feeding outlined in the relevant SmPCs and Appendix 6 must be followed. Highly effective contraceptive measures must be used by both female participants of child bearing potential and male participants (see Appendix 6 for details of appropriate contraception). Female participants of child bearing potential must use highly effective contraceptive measures throughout the study and for 3 months after stopping treatment. Male participants must use appropriate contraception throughout the study and for 3 months after stopping treatment.

Participants who are randomised to the pausing ibrutinib arm will not be required to follow contraceptive measures whilst on treatment breaks, but must continue to follow contraceptive measures for 3 months after stopping treatment for each treatment break. Contraceptive measures

must restart once treatment with ibrutinib resumes. Participants who become pregnant during a treatment break will come off trial treatment.

All protocol therapy must be stopped immediately if a pregnancy in a female participant occurs or is suspected, including during a treatment break in the pausing ibrutinib arm. Participants must be instructed to return any unused portion of the medication to the investigator. Participants withdrawn from treatment will still attend for follow-up assessments unless unwilling to do so and case report forms will continue to be collected.

Female participants should be referred to an obstetrician/gynaecologist experienced in reproductive toxicity for further evaluation and counselling. If a pregnancy occurs in a male participant's partner, the partner should be advised to consult her GP or gynaecologist as soon as possible.

Breast-feeding must be discontinued during treatment with ibrutinib.

The local PI shall be responsible for any decision regarding the continued participation in the study of participants who, after an initial positive pregnancy diagnosis, are confirmed as no longer being pregnant.

